8.1.3. Serious Adverse Events

In addition to the tabular summaries of SAEs described in Section 8.1, listings will be provided by subject for all SAEs [L3.03] and all deaths [L3.04]. The cause of death will be categorized by GSK.

A listing will be provided by subject to display the reason(s) why each SAE was considered Serious [L3.06].

8.1.4. AE outputs required for Mexico

The number and percentage of subjects experiencing SAEs will be presented by Country and Preferred Term [T3.43], both overall and by gender.

The number and percentage of subjects experiencing AEs will be presented by Preferred Term [T3.44], both overall and by Seriousness (Serious/Non-Serious).

A listing of all non-serious AEs for subjects in Mexico will be presented for the Enrolled population [T3.45].

A listing of all SAEs for subjects in Mexico will also be presented for the Enrolled population [T3.46].

8.1.5. Adverse Events of Special Interest (AESI) Analyses

To ensure consistency across belimumab studies, AESI will be defined per the version of the Benlysta Program Safety Analysis Plan (PSAP) and MedDRA in effect at the time of DBL.

The Benlysta PSAP has been developed to include an AESI analysis for consistent reporting across belimumab studies. Categorizations for the AESIs will be defined in the PSAP.

The milestone defined in the PSAP for categorizations will be the first DBL, for the primary analysis (Section 3.2).

Events will only be reported once even if the event does not resolve by the Week 52 visit.

An overall summary of AESIs will be presented and each specific category of AESI will be presented separately by PT [T3.12]. The number and percentage of subjects with at least one occurrence and the number of events will be provided.

The following AESI will be identified and categorized as detailed in the PSAP.

Adverse Events

Adverse Events of Special Interest (AESI)

AESI will be defined per the version of the PSAP/MedDRA in effect at the time of DBL.

Malignant Neoplasms

- Malignancies Excluding non-melanoma skin cancer (NMSC)
- Malignancies Including NMSC
 - Solid Tumour
 - Hematologic
 - Skin (All)
 - NMSC
 - Excluding NMSC
 - Tumours of unspecified malignancy categorized as malignant per GSK

Post-Injection Systemic Reactions (PISR)

- PISR per Anaphylactic Reaction Customized MedDRA Query (CMQ) narrow search
- PISR per Anaphylactic Reaction CMQ broad search
- PISR per Anaphylactic Reaction CMQ algorithmic search
- Serious Anaphylaxis per Sampson Criteria per GSK categorization
- Serious Acute PISR/Hypersensitivity Per GSK categorization
 - Serious Acute PISR Excluding Hypersensitivity per GSK categorization
 - Serious Acute Hypersensitivity Reactions per GSK categorization
- Serious Delayed Acute Hypersensitivity Reactions per GSK categorization
- Serious Delayed Non-Acute Hypersensitivity Reactions per GSK categorization

All Infections of Special Interest (Opportunistic Infections (OI), Herpes Zoster (HZ), Tuberculosis (TB), And Sepsis; All and Serious, separately)

- All opportunistic infections (OI) per GSK categorization
- OI per GSK categorization excluding Tuberculosis and Herpes Zoster
- Active Tuberculosis
 - Non-Opportunistic
 - Opportunistic
- Herpes Zoster
 - Non-Opportunistic
 - Opportunistic
 - Recurrent
 - Disseminated
- Sepsis

Adverse Events

Adverse Events of Special Interest (AESI)

Depression (including mood disorders and anxiety)/suicide/self-injury (All and Serious, separately)

- Depression (including mood disorders and anxiety) (excluding suicide and self-injury)
- Suicide/self-injury
- Serous suicide/self-injury per GSK categorization
 - Suicidal Behavior
 - Completed Suicide
 - Suicidal Ideation
 - Self-injurious Behavior without Suicidal Intent
- Deaths

Malignant neoplasm events identified as "tumours of unspecified malignancy" will be reviewed for classification as malignant per GSK categorization and will be presented by category and PT.

Post-injection systemic reactions and serious post-injection systemic reactions will be presented using nine different definitions as indicated above.

Infection AESIs will be presented by Category and PT for all infections and for infections leading to study drug discontinuation.

Depression, suicide and self-injury as defined in the PSAP will be presented by Category and PT.

All AESI will be presented in a listing by AESI subcategory and subject [L3.07].

A comprehensive list of MedDRA terms based on clinical review will be used to identify each type of event. Changes to the MedDRA dictionary may occur between the start of the study and the time of reporting and/or emerging data from on-going studies may highlight additional AESI, therefore the list of terms to be used for each event of interest and the specific events of interest will be based on the safety review team (SRT) agreements in place at the time of reporting.

8.1.5.1. Injection/Anaphylaxis/Hypersensitivity Reactions by Infusion

Summaries of injection, hypersensitivity, and anaphylactic reactions that occur in relation to the first six injections will be presented by each injection and PT for the following:

- Post-Injection Systemic Reactions per Anaphylactic Reactions CMQ Broad Search by PT, in First Six Injections [T3.13]
- Serious Post-Injection Systemic Reactions per Anaphylactic Reaction CMQ Broad search by PT, in First Six Injections [T3.14]

- Serious Acute Post-Injection Systemic Reactions/Hypersensitivity per GSK Categorization by PT, in First Six Injections [T3.15]
- Serious Delayed Acute Hypersensitivity Reactions per GSK Categorization by PT, in First Six Injections [T3.16]
- Serious Delayed Non-Acute Hypersensitivity Reactions per GSK Categorization by PT, in First Six Injections [T3.17]

8.2. Clinical Laboratory Analyses

Laboratory evaluations including the analyses of Chemistry laboratory tests, Hematology laboratory tests, Urinalysis and liver function tests will be based on GSK Core Data Standards.

For laboratory analyses, analytes will be summarized and analyses will be performed based on the observed data, no imputation will be done for missing data. Baseline is defined as described in Section 5.4.

Laboratory toxicity will be graded using the Adverse Event and Laboratory Value Severity Grading Table (see Protocol Appendix 2, Section 10.2.1). The Table is based upon publicly available Tables from the National Institute of Allergy and Infectious Disease Division of Microbiology and Infectious Diseases (www.niaid.nih.gov) and Common Terminology Criteria for Adverse Events (CTCAE) Version 4.0 (U.S. Department of Health and Human Services, 2010). Toxicity grades provided by the laboratory will be used. Any laboratory parameters where toxicity grades are expected but not provided by the laboratory will be programmed according to the Protocol.

If a numeric laboratory value, has a non-detectable level reported in the database, then typically the numeric value is missing, and a character value starting with '<x' or '>x' is present. A numeric value will be derived using the number of decimal places in the observed character values i.e.

- 2 Decimal Places = '<x' becomes x-0.01
- 1 Decimal Place = '>x' becomes x+0.1
- 0 Decimal places = '<x' becomes x-1

Laboratory parameters are shown in Table 5, split by output category (hematology, liver function, electrolytes, other chemistries, urinalysis and immunoglobulins) and indicating which type of outputs are applicable for each parameter.

Table 5 Laboratory Parameters

Laboratory Parameter	Lab Results by Visit (Section 8.2.1)	Toxicity Grade (Section 8.2.2 and Section 8.2.3)	Reference Range Shifts (Section 8.2.4)
Hematology		 	
Basophils (10^9/L)	Yes		Yes
Basophils/Leukocytes (%)	Yes		Yes
Eosinophils (10^9/L)	Yes		Yes
Eosinophils/Leukocytes (%)	Yes		Yes
Ery. Mean Corpuscular Hemoglobin (pg)	Yes		Yes
Ery. Mean Corpuscular Volume (fL)	Yes		Yes
Erythrocytes (10^12/L)	Yes		Yes
Hematocrit (%)	Yes		Yes
Hemoglobin (g/L)	Yes	Yes	
Leukocytes (10^9/L)	Yes	Yes	
Lymphocytes (10^9/L)	Yes	Yes	
Lymphocytes/Leukocytes (%)	Yes		Yes
Monocytes (10^9/L)	Yes		Yes
Monocytes/Leukocytes (%)	Yes		Yes
Neutrophils (10^9/L)	Yes	Yes	
Neutrophils, Segmented (10^9/L)	Yes		Yes
Neutrophils, Segmented/Leukocytes (%)	Yes		Yes
Neutrophils/Leukocytes (%)	Yes		Yes
Platelets (10^9/L)	Yes	Yes	
% Reticulocytes (%)	Yes		Yes
Liver Function			
Alanine Aminotransferase (U/L)	Yes	Yes	
Alkaline Phosphatase (U/L)	Yes	Yes	
Aspartate Aminotransferase (U/L)	Yes	Yes	
Bilirubin (umol/L)	Yes	Yes	
Direct Bilirubin (umol/L)	Yes		Yes
Gamma Glutamyl Transferase (U/L)	Yes	Yes	
Electrolytes			
Calcium (mmol/L)	Yes		Yes
Calcium Corrected for albumin (mmol/L)	Yes		
Calcium corrected for albumin - Hypercalcemia (mmol/L)		Yes	
Calcium corrected for albumin - Hypocalcemia (mmol/L)		Yes	
Carbon Dioxide (mmol/L)	Yes		Yes
Magnesium (mmol/L)	Yes	Yes	
Phosphate (mmol/L)	Yes	Yes	
Potassium (mmol/L)	Yes		
Potassium - Hyperkalemia (mmol/L)		Yes	
Potassium - Hypokalemia (mmol/L)		Yes	
Sodium (mmol/L)	Yes		
Sodium - Hypernatremia (mmol/L)		Yes	
Sodium - Hyponatremia (mmol/L)		Yes	
Other Chemistries			

Laboratory Parameter	Lab Results by Visit (Section 8.2.1)	Toxicity Grade (Section 8.2.2 and Section 8.2.3)	
Albumin (g/L)	Yes	Yes	
Creatinine (umol/L)	Yes	Yes	
GFR from Creatinine Adjusted for BSA (mL/sec/1.73m2)	Yes		Yes
Glucose (mmol/L)	Yes		
Glucose - Hyperglycemia (mmol/L)		Yes	
Glucose - Hypoglycemia (mmol/L)		Yes	
Protein (g/L)	Yes		Yes
Urate (umol/L)	Yes	Yes	
Urea (mmol/L)	Yes		Yes
Urea Nitrogen/Creatinine	Yes		Yes
Urinalysis			
Erythrocytes		Yes	
Protein (Dipstick)		Yes	
Protein/Creatinine (mg/mg)		Yes	
Leukocytes			Yes
рН			Yes
Immunoglobulins	_		
Immunoglobulin G (g/L)		Yes	

Listings will be generated for all laboratory results for hematology [L3.12], liver function [L3.13], electrolytes [L3.14], other chemistries [L3.15], urinalysis [L3.16] and immunoglobulins [L3.17].

Listings will also be generated for all Grade 3 or Grade 4 laboratory toxicity results for hematology [L3.18], liver function [L3.19], electrolytes [L3.20], other chemistries [L3.21], urinalysis [L3.22] and immunoglobulins [L3.23]. If a subject has a lab parameter where a Grade 3 or 4 result is obtained at any visit, all of the data for that subject and that lab parameter will be presented at all visits.

8.2.1. Laboratory Assessments by Visit

Descriptive summary statistics for each laboratory parameter will be displayed for each visit, for hematology [T3.18], liver function [T3.19], electrolytes [T3.20] and other chemistries [T3.21]. No statistical tests will be performed.

A line graph will be produced for each lab parameter which displays the mean value (±SE) by visit for hematology [F3.01], liver function [F3.02], electrolytes [F3.03] and other chemistries [F3.04].

8.2.2. Worst Laboratory Toxicity Grade Post-baseline

The worst laboratory toxicity grade post-baseline (including unscheduled visits and follow up assessments) will be presented for each laboratory parameter within

hematology [T3.22], liver function [T3.23], electrolytes [T3.24], other chemistries [T3.25], urinalysis [T3.26] and immunoglobulins [T3.27].

8.2.3. Laboratory Toxicity ≥ 2 Grade Worsening Post-Baseline

Toxicity grade worsening of ≥ 2 grades from baseline will be summarized post-baseline (including unscheduled visits and follow up assessments) for each laboratory parameter with toxicity grades within hematology [T3.28], liver function [T3.29], electrolytes [T3.30], other chemistries [T3.31], urinalysis [T3.32] and immunoglobulins [T3.33]).

The tables will display the number and percentage of subjects with at least one ≥ 2 grade shift as well as the specific shift categories: Grade 0 to 2, Grade 0 to 3, Grade 0 to 4, Grade 1 to 3, Grade 1 to 4 and Grade 2 to 4.

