11. Have a Grade 3 or greater laboratory abnormality based on the protocol defined Adverse Event and Laboratory Value Severity Grade scale ([Appendix 2](#), Section [10.2.1](#)) except for the following that are allowed:
 - Stable Grade 3 prothrombin time (PT) secondary to warfarin treatment.
 - Stable Grade 3 partial thromboplastin time (PTT) due to lupus anticoagulant and not related to liver disease or anti-coagulant therapy.
 - Stable Grade 3 hypoalbuminemia due to lupus nephritis, and not related to liver disease or malnutrition.
 - Any grade proteinuria.
 - Stable Grade 3 gamma glutamyl transferase (GGT) elevation due to lupus hepatitis, and not related to alcoholic liver disease, uncontrolled diabetes or viral hepatitis. If present, any abnormalities in the ALT and or AST must be \leq Grade 2.
 - Stable Grade 3 neutropenia; or stable Grade 3 lymphopenia; or stable Grade 3 leukopenia, due to SLE.
12. Have a history of an anaphylactic reaction to parenteral administration of contrast agents, human or murine proteins or monoclonal antibodies or to any of the excipients of the study drug.

Prior/Concomitant Therapy

13. Have ever received treatment with belimumab (BENLYSTA).
14. Have received any of the following within 364 days of Day 1:
 - Treatment with any B-cell targeted therapy (e.g., rituximab, other anti-CD20 agents, anti-CD22 [epratuzumab], anti-CD52 [alemtuzumab], BLyS-receptor fusion protein [BR3], TACI-Fc)
 - Abatacept.
 - Any biologic investigational agent
15. Have required 3 or more courses of systemic corticosteroids for concomitant conditions (e.g., asthma, atopic dermatitis) within 90 days of Day 1 (topical or inhaled steroids are permitted).
16. Have received any of the following within 90 days of Day 1:

- Anti-TNF therapy (e.g., adalimumab, etanercept, infliximab).
- Interleukin-1 receptor antagonist (anakinra).
- Intravenous immunoglobulin (IVIG).
- Plasmapheresis.

17. Have received any of the following within 30 days of Day 1:

- Intravenous (IV) cyclophosphamide.
- A non-biologic investigational agent (30 day window OR 5 half-lives, whichever is greater).
- Any new immunosuppressive/immunomodulatory agent.
- High dose prednisone or equivalent (>1.5 mg/kg/day) or any intramuscular or intravenous steroid injection.
- Note: New inhaled steroids, intraarticular steroids, and new topical immunosuppressive agents (e.g., eye drops, topical creams) are allowed. Any NSAID use for < 1 week is allowed.

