8.2.4. Laboratory Reference Range Shifts from Baseline by Visit

For laboratory tests without toxicity grades, shifts relative to the normal range will be summarized for each lab parameter within hematology [T3.34], liver function [T3.35], electrolytes [T3.36], other chemistries [T3.37] and urinalysis [T3.38]. No statistical tests will be performed.

For the 'shift to low' category, the percentage of subjects with at least one low post-baseline value will be displayed using the categories: 'remained low' and 'shift normal/high to low'.

For the 'shift to normal/high' category, the percentage of subjects with at least one normal/high post-baseline value will be displayed using the categories: 'remained normal/high' and 'shift low to normal/high'.

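### No summary table in the SAP shows one-grade worsening into Grade 3 or 4 against baseline, and on seven laboratory lines the worst-grade tables do not separate new from entry abnormalities

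*SAP*

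**What the plan says.** Three parts of the SAP deal with graded laboratory results.

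- **Worst grade (8.2.2, T3.22-T3.27).** "The worst laboratory toxicity grade post-baseline (including unscheduled visits and follow up assessments) will be presented for each laboratory parameter within" six categories, from hematology to immunoglobulins. The text mentions no baseline grade.
- **Worsening (8.2.3, T3.28-T3.33).** "Toxicity grade worsening of ≥ 2 grades from baseline will be summarized post-baseline", with the shift rows named as 0 to 2, 0 to 3, and then "Grade 0 to 4, Grade 1 to 3, Grade 1 to 4 and Grade 2 to 4".
- **Listings (8.2, L3.18-L3.23).** "Listings will also be generated for all Grade 3 or Grade 4 laboratory toxicity results", and once a child has such a result, "all of the data for that subject and that lab parameter will be presented at all visits".

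The reference-range shifts do not reach graded tests: "For laboratory tests without toxicity grades, shifts relative to the normal range will be summarized" (8.2.4).

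On entry, Protocol 5.2 exclusion criterion 11 bars Grade 3 or greater abnormalities but makes exceptions. One is "Stable Grade 3 neutropenia; or stable Grade 3 lymphopenia; or stable Grade 3 leukopenia, due to SLE". Others allow stable Grade 3 hypoalbuminemia from lupus nephritis, stable Grade 3 GGT from lupus hepatitis, and proteinuria of any grade. The PT and PTT exceptions do not matter here, because neither test is in SAP Table 5.

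**The concern.** The study has one arm, so a child's own baseline is the only within-study reference for deciding whether a severe laboratory value is new. The protocol deliberately admits children whose lupus already puts some values at Grade 3, or at any grade for proteinuria. Neutrophils are among these lines, and Protocol 2.2.1.4 names neutropenia as an event reported at least 3% more often on IV belimumab than on placebo in the pediatric IV trial.

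The two sets of graded tables each leave out half of what is needed. The worsening tables use baseline but drop one-grade moves. The worst-grade tables keep every severe value but, as described, drop baseline. A Grade 3 neutrophil count that was present at entry and never changed therefore sits in the same cell as one that fell from Grade 2 on treatment.

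**Working it through.** No sample size, power or alpha enters this point. The check is an enumeration, followed by tracing cases through the planned tables.

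**1. Shifts covered.** On a 0-4 scale there are 4 + 3 + 2 + 1 = 10 worsening moves. Those of two or more grades number 3 + 2 + 1 = 6, and they match the SAP's six rows exactly, so the list is complete for its own rule.

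**2. Moves that end in Grade 3 or 4.** Into Grade 3: 0-3, 1-3, 2-3. Into Grade 4: 0-4, 1-4, 2-4, 3-4. Total 3 + 4 = 7. Five have a row (0-3, 1-3, 0-4, 1-4, 2-4). Two do not: 2-3 and 3-4. From Grade 3 the only worse grade is 4, one step up, so a Grade 3 entrant can never qualify on that line.

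**3. Lines where entry and new values can be confused.** Graded lines in SAP Table 5: hematology 5, liver function 5, electrolytes 8, other chemistries 5, urinalysis 3, immunoglobulins 1; total 27. Criterion 11 exempts 7 of them: neutrophils, lymphocytes, leukocytes, GGT, albumin, dipstick protein and protein:creatinine. For the first five only Grade 3 is allowed at entry, so the ambiguity is in the Grade 3 row. For the two proteinuria lines it affects both the Grade 3 and Grade 4 rows. On the remaining 27 - 7 = 20 lines, a post-baseline Grade 3 or 4 is new relative to eligibility, barring an entry deviation or a value that had already reached Grade 3 by Day 1.

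**4. Two cases traced, using the grades in Protocol 10.2.1.**

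| Table | Protein:creatinine 2.5 to 6.0 mg/mg (Grade 3 to 4) | IgG 410 to 260 mg/dL (Grade 2 to 3) |
|---|---|---|
| Worst grade | Grade 4 in T3.26 | Grade 3 in T3.27 |
| Worsening by 2 or more grades | Absent from T3.32 | Absent from T3.33 |
| Single cut-off shift | T2.04 cuts at 0.5 mg/mg: high both times, so no change | T4.03 cuts at the LLN: a shift only if the LLN is above 260 and at most 410; otherwise no change (LLN not given) |
| Listing | L3.22, all visits | L3.23, all visits |

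Both children are counted as severe; neither is tabulated as having worsened by grade. The IgG case is the milder problem, because IgG has no entry exception and a Grade 3 value already implies a fall since eligibility. The proteinuria case could equally be a child who entered at Grade 4 and stayed there.

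**5. Size.** With about 28 enrolled and treated (Protocol 9.2), one child is 1/28 = 3.6 percentage points. The documents do not say how many children will enter at a permitted Grade 3 or higher. Taking 1 to 5 on a given line as an assumed range, unchanged entry values would add 1/28 = 3.6% to 5/28 = 17.9% to the severe rows.

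**6. After the change.** Adding 2-3 and 3-4 takes coverage of worsening into Grade 3 or 4 from 5 of 7 moves to 7 of 7. A 5 by 5 table of baseline by worst grade does the same and also isolates the unchanged cells 3-3 and 4-4.

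**The case against.** The strongest reply is that little is really lost. Grade 2 to 4 has its own row. Children who move 2 to 3 or 3 to 4 are counted in the worst-grade tables. The listings show every visit for every child with a Grade 3 or 4 result on a line, and with about 28 children that is a short read. Clinically significant laboratory changes can also be recorded as adverse events and summarized by severity (T3.10). A threshold of two grades is a coherent display rule, the study is descriptive, and the secondary safety endpoint is adverse events rather than laboratory grades. The mock shells, which might show a baseline column, are not among the documents.

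Most of this stands, and it limits the point. It rules out the reading that new severe toxicity goes uncounted: the count is there, and what is missing is the label that it is new. It also rules out extending the problem to every analyte, since on 20 of 27 lines eligibility already makes a severe value new. A reader might further infer that the plan presents entry abnormalities as drug toxicity. The SAP attributes nothing in these tables to drug; it only leaves the two kinds of value unseparated.

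What the reply does not supply is a prespecified count. A listing has to be reclassified by hand after the data are seen. The adverse event route depends on investigator judgement, and Protocol 10.3.1 leaves out findings associated with the underlying disease unless they are more severe than expected, which is the setting of the exempted lines.

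**Conclusion.** The point holds as a gap in presentation with a cheap remedy; the planned tables are incomplete, not wrong. No summary table described in the SAP identifies worsening from Grade 2 to 3 or from 3 to 4 against baseline: 2 of the 7 moves into Grade 3 or 4. On the seven exempted lines the worst-grade tables, as described, mix new with entry abnormalities, at 3.6 percentage points per child.

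This rests on three assumptions: that the shells for T3.22-T3.27 follow the SAP text and have no baseline dimension, that about 28 children form the denominator, and that some children do enter under the exceptions. If the shells already cross-classify by baseline grade, only the SAP wording needs to say so.

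**What to change.** Either of two changes is enough.

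- Present T3.22-T3.27 as baseline grade (0-4) by worst post-baseline grade (0-4) for each line. This is the better option, because it also separates unchanged entry values.
- Or keep those tables and add to T3.28-T3.33 a row for any worsening from baseline to Grade 3 or 4, stating that it includes 2 to 3 and 3 to 4.

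Baseline is already defined in SAP 5.4 and the grades are already planned, so no new data are needed. The cost is a sentence in SAP 8.2.2 or 8.2.3, a revised shell, minor programming and slightly larger tables. The Grade 3/4 listings stay as they are.

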8.2.4. Laboratory Reference Range Shifts from Baseline by Visit

For laboratory tests without toxicity grades, shifts relative to the normal range will be summarized for each lab parameter within hematology [T3.34], liver function [T3.35], electrolytes [T3.36], other chemistries [T3.37] and urinalysis [T3.38]. No statistical tests will be performed.

For the 'shift to low' category, the percentage of subjects with at least one low post-baseline value will be displayed using the categories: 'remained low' and 'shift normal/high to low'.

For the 'shift to normal/high' category, the percentage of subjects with at least one normal/high post-baseline value will be displayed using the categories: 'remained normal/high' and 'shift low to normal/high'.

